6.4 Primary Safety Endpoints

The study design evaluates the potential to substitute non-invasive for invasive FFR. Safety endpoints of the study include: 1. Evaluating the diagnostic accuracy of non-invasive FFR. If the end result demonstrates that the procedure is less accurate than invasive FFR, patients receiving this procedure, as an alternative to the current standard will be at greater risk. 2. Patients who undergo invasive procedures experience increased risk of infection or other comorbidities or complications, as compared to those who do not undergo invasive procedures. Therefore, if the noninvasive protocol results are not significantly different than the invasive results, patient safety might potentially be increased by using the noninvasive technology. 3. Noninvasive technology has the potential to reduce radiation exposure by reducing the number of invasive angiography and Stress MPI procedures necessary to complete patient evaluation. This increases patient safety relative to the adverse effects of radiation exposure.

7 Subject Selection and Withdrawal

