14.2 Statistical Methods

Statistical Aims

1. *To determine the sensitivity, specificity, positive predictive value (PPV) and negative predictive value (NPV) of the CCTA test (with or without stress MPI, as specified in Figure 1) + CT-FFR evaluation to identify chest pain patients with flow-limiting obstructive CAD. The ICA test will be used as gold standard.*
2. *To determine inter-observer reliability of CCTA and CCTA+CT-FFR test readings between an experienced and a non-experienced reader, and compare the results between CCTA and CCTA+CT-FFR; to determine the intra-observer reliability of CCTA and CCTA-FFR reading, for both the experienced and non-experienced reader, and for each reader compare the results between CCTA and CCTA+CT-FFR.*

3. To identify factors of return visit within 90 days in patients who had no ICA test or a negative ICA test result.

Outcome Variables

- *CCTA+CT-FFR test status (Positive/Negative). The test is deemed positive if ICA is required and negative if ICA is not required (see Figure 1).*
- *ICA (gold standard) test status (Positive / Negative). ICA is deemed positive if $FFR < 0.8$ and vessel diameter $>= 2\text{mm}$ or if the patient requires revascularizations based on invasively estimated stenosis severity. It is deemed negative otherwise.*
- *Return visit within 90 days (Y/N). Return visit is defined as patients who return for unplanned cardiac care, including emergency room visits, emergency hospital admissions, urgent percutaneous coronary intervention, coronary artery bypass graft, or acute myocardial infarction. Descriptive statistics (n, mean, median, standard deviation, IQR, frequencies and percentages) will be used to describe the demographic and clinical characteristics of the whole sample.*

For Aim 1, sensitivity, specificity, PPV, and NPV will be computed using the ICA result as the ‘true’ flow-limiting obstructive CAD status and the CCTA+CT-FFR test result as the ‘test’ status. Exact binomial 95% confidence intervals will be computed.

For Aim 2, inter- and intra-observer reliability for the CCTA and CCTA+CT-FFR tests will be assessed using Cohen’s Kappa coefficient. Dependent Kappa coefficients will be compared using a method developed by Donner et al .

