15.1 Definitions

Adverse Event

An **adverse event** (AE) is any symptom, sign, illness or experience that develops or worsens in severity during the course of the study, as a result of study activities. Intercurrent illnesses or injuries will be regarded as adverse events. Abnormal results of diagnostic procedures are considered to be adverse events if the abnormality:

- results in study withdrawal
- is associated with a serious adverse event
- is associated with clinical signs or symptoms
- leads to additional treatment or to further diagnostic tests
- is considered by the investigator to be of clinical significance

Serious Adverse Event

Adverse events are classified as serious or non-serious. A **serious adverse event** is any AE that is:

- fatal
- life-threatening
- requires or prolongs hospital stay
- results in persistent or significant disability or incapacity
- an important medical event

Important medical events are those that may not be immediately life threatening, but are clearly of major clinical significance. They may jeopardize the subject, and may require intervention to prevent one of the other serious outcomes noted above. For example, drug overdose or abuse, a seizure that did not result in in-patient hospitalization, or intensive treatment of bronchospasm in an emergency department would typically be considered serious.

All adverse events that do not meet any of the criteria for serious will be regarded as **non-serious adverse events**.

Adverse Event Reporting Period

The study period during which adverse events must be reported will be defined as the period from the initiation of any study procedures to the end of the study treatment follow-up. For this study, the study treatment follow-up is defined as 90 days following the last administration of study treatment.

Preexisting Condition

A preexisting condition is one that is present at the start of the study. Preexisting conditions will be recorded as an adverse event if the errors in diagnosis cause less than optimal treatment decisions.

General Physical Examination Findings

At screening, any clinically significant abnormality will be recorded as a preexisting condition. At the end of the study, any new clinically significant findings/abnormalities that were not diagnosed through the study protocol will meet the definition of an adverse event and will also be recorded and documented as an adverse event.

Post-study Adverse Event

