All unresolved adverse events should be followed by the investigator until the events are resolved, the subject is lost to follow-up, or the adverse event is otherwise explained.

Hospitalization, Prolonged Hospitalization or Surgery

Any adverse event that results in hospitalization or prolonged hospitalization will be documented and reported as a serious adverse event. Any condition responsible for surgery will be documented as an adverse event if the condition meets the criteria for an adverse event.

Neither the condition, hospitalization, prolonged hospitalization, nor surgery will be reported as an adverse event in the following circumstances:

- Hospitalization or prolonged hospitalization for diagnostic or elective surgical procedures for a preexisting condition. Surgery will **not** be reported as an outcome of an adverse event if the purpose of the surgery was elective or diagnostic and the outcome was uneventful.
- Hospitalization or prolonged hospitalization for therapy of the target disease of the study, unless it is the result of inaccurate diagnostic information provided in the study.

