15.7.1 Data and Safety Monitoring Plan

[name]. will conduct data safety monitoring for the study.

His role as Director of the Cardiac Catheterization program at Lenox Hill Hospital makes him the most appropriate person to review the study safety, because he will have the most complete information on the cardiovascular condition of the patient, and the patients response to invasive ICA, the primary study activity that has potential to influence patient safety.

The expected types of events that will be monitored include major adverse cardiac events resulting from any Cardiac Catheterization, Percutaneous Coronary Intervention, or Coronary Artery Bypass Graft in a patient who, if not enrolled in the study, would not have received Cardiac Cath or invasive treatments. In addition, the monitor will review any medical complications for these subjects. The study coordinator will refer all patients who received Cardiac Cath, who would not have otherwise have received it if not part of the study. The monitor will review whether adverse events were the result of the study activity or related to procedures provided as part of standard of care, and whether safety policies and procedures were followed within one week of the all referrals. The monitor will present any recommendations for changes to the study resulting from the review to the study PI.

The monitor will conduct reviews as near as possible to the time the event was identified and always within a month of the identification of the event.

We do not expect to need to alter or interrupt the study design, because of the very low risk nature of the study. However, any unexpected safety events related to the study design will be carefully reviewed by the Safety Monitor and the study PI and reported to the IRB and Hospital quality assurance. If improvement in patient safety can be made by changing the design, immediate consideration will be given to the prospective change.

There are no issues with toxicity in this study.

If the study should be temporarily suspended, we will report this to the IRB, Clinical trials.gov, and to HeartFlow.

16 Data Handling and Record Keeping

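### Coronary admissions are reported as adverse events only after being attributed to a wrong study reading, and the monitor is not sent patients managed without ICA, so missed-disease events can be under-reported

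*Combined protocol and SAP*

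**What the plan says.** Section 6.4 puts the diagnostic accuracy of non-invasive FFR first among the safety endpoints. It reasons that "If the end result demonstrates that the procedure is less accurate than invasive FFR", patients who receive it in place of the current standard face more risk.

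Section 15.1 then sets the reporting rules. An adverse event is one that "develops or worsens in severity during the course of the study, as a result of study activities". Two circumstances are carved out, and in both the underlying condition goes unreported as well as the admission. The second is "Hospitalization or prolonged hospitalization for therapy of the target disease of the study, unless it is the result of inaccurate diagnostic information provided".

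Section 15.7.1 describes what the safety monitor reviews: "major adverse cardiac events resulting from any Cardiac Catheterization, Percutaneous Coronary Intervention, or Coronary Artery Bypass Graft in a patient who, if not enrolled", would not have had these procedures. The coordinator's referrals are limited to patients with such an extra catheterization. A further sentence has unanticipated safety events tied to the study design reviewed by the monitor and the principal investigator and sent to the IRB.

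Section 14.2 defines a 90-day outcome for Aim 3: "Return visit is defined as patients who return for unplanned cardiac care, including emergency room visits, emergency hospital admissions, urgent percutaneous coronary intervention", bypass surgery or acute infarction. Aim 3 studies it in patients with no ICA or a negative ICA. The only use specified is a time-to-event regression.

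**The concern.** If CT-FFR is less accurate than hoped, the patient-level harm is missed disease: someone is sent to medical follow-up and later has an infarction or an urgent revascularization. That is an admission for the disease under study, so Section 15.1 leaves it unreported unless someone first decides that a study reading was wrong. The protocol does not say who decides, by what criteria, or when.

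The judgement is hardest where it matters most. Section 14.2 makes ICA the gold standard and defines a negative test as one after which ICA is not required. Test-negative patients therefore have no planned reference result.

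At stake is what a low count of serious adverse events would mean. It could reflect safe triage, or it could reflect a rule that asks for attribution before reporting. A cluster of such events during the ten-month recruitment period might also not reach the monitor.

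**Working it through.** **1. Reproducing the plan's figure.** Inputs from Section 14.1: p0 = 0.14, p1 = 0.06, two-sided alpha 0.05, power 80%, one-sample test.

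n = [(1.96 × √(0.14 × 0.86) + 0.8416 × √(0.06 × 0.94)) / 0.08]² = 120.99, so 121 patients with ICA, as stated.

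Total: 121 / (0.60 × 0.35) = 576.2, matching the stated 576. The same proportions can therefore be used to size the group without ICA.

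**2. Patients without a planned reference test.**
- With CT-FFR: 576 × 0.60 = 345.6, about 346.
- With ICA: 345.6 × 0.35 = 120.96, about 121.
- CT-FFR without ICA: 345.6 − 121 = 224.6, about 225, or 65% of those with CT-FFR.
- All enrolled patients without ICA: 576 − 121 = 455, or 79%.

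**3. Possible number of events.** The documents give no 90-day rate of unplanned coronary admission. Assumed rates among the 225:
- 0.5%: 1.1 events
- 1%: 2.25 events
- 2%: 4.5 events
- 3%: 6.75 events

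If no event were reported among 225, the exact two-sided 95% upper limit for the rate would be 1 − 0.025^(1/225) = 1.6%. In the extreme case where every event went unattributed, a true rate of 3% (about 7 events) would be presented as a rate below 1.6%. With numbers this small, the classification of one or two events shapes the safety conclusion.

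**4. Other routes by which such an event could be reported.**
- *Pre-existing conditions (Section 15.1).* "Preexisting conditions will be recorded as an adverse event if the errors in diagnosis cause less than optimal treatment decisions". This reaches missed disease, but it too requires a finding that a diagnosis was in error.
- *New findings (Section 15.1).* "any new clinically significant findings/abnormalities that were not diagnosed through the study protocol will meet the definition of an adverse event". This needs no finding of error, but it applies at the end of the study and stands under physical examination findings. Section 9 schedules no closing examination, and Section 8.6 describes an interview at 90 to 120 days. The protocol does not say whether this rule or the target-disease exclusion prevails when both apply.
- *Late events (Section 15.2).* Serious events possibly related to participation are reported immediately. That is a lower threshold, but it covers only events after the study period.
- *SAE review (Sections 15.3.2 and 15.6).* The IRB receives all serious adverse events, and their number and type are assessed regularly. Both act only on events already classified as adverse events.
- *Monitor's general clause (Section 15.7.1).* It covers unanticipated events tied to the design, so attribution again comes first, and no referral step is given for patients without ICA.
- *Aim 3 (Section 14.2).* It captures the events, but no route to the monitor or IRB is described.

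Each route catches some events. None reports an unplanned coronary admission during the study period simply because it occurred.

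**The case against.** The strongest reply is that the exception was written for exactly this case: an admission caused by a false-negative reading is expressly reportable. A reader might infer that missed-disease harm drops out of safety reporting altogether. The documents do not support that, because the exception, the two further rules in Section 15.1 and the general clause in Section 15.7.1 all keep attributed cases in.

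A reader might also infer that inaccuracy cannot be established in a patient without ICA. That is too strong as well. A patient later admitted for urgent intervention may have angiography then, and Section 14.2 counts a need for revascularization as a positive ICA, so the earlier reading can be checked. Nor do the documents say that the team that made the reading decides; they name nobody.

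A third argument is that a negative CT-FFR changes little care. Section 6.1 already sends the 30% to 49% group to follow-up. Section 8.3 sends negative results at 50% to 70% to stress MPI or to reliance on a recent stress test, and sends the highest stenosis group to ICA regardless. Extra catheterization is thus the more visible added risk, and the monitor's remit matches it. This stands as a limit on size: 225 is the number without a planned reference test, not the number whose care changed or whose events would be excluded. It is not complete, because Section 9 says that usual practice for borderline disease leaves the choice between stress testing and ICA to the cardiologist, so a negative result could influence some decisions.

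What remains is that reporting depends on an attribution with no criteria and no named decision-maker, and that routine referral to the monitor omits patients managed without ICA.

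**Conclusion.** The point holds as a risk of under-reporting, not as a total loss of safety information. Non-reporting is the default for target-disease admissions, and the exception rests on an undefined judgement of diagnostic inaccuracy. The monitor is routinely sent only patients with an extra catheterization. Missed-disease events can therefore be under-counted as serious adverse events and missed by the monitor while patients are still being enrolled.

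The group concerned is about 225 of 346 CT-FFR patients, provided the Section 14.1 proportions hold. The 1 to 7 events rest on an assumed rate of 0.5% to 3%. How many would actually go unreported cannot be derived from the documents. The change is worth making because accuracy is the first safety endpoint and the outcome is already being collected.

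**What to change.** - **Section 15.1:** limit the target-disease exclusion to planned admissions that follow from the study pathway. Report every unplanned cardiac return within 90 days, as already defined in Section 14.2, as an adverse event, or as a serious adverse event if the patient is hospitalized, with no prior judgement on diagnostic accuracy.
- **Section 15.7.1:** add these events in patients managed without ICA to the coordinator's referral list, with the CCTA, CT-FFR and any stress MPI results attached. Diagnostic inaccuracy is then judged at review and is no longer a condition for reporting.

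This changes reporting only, not patient management. It costs some protocol wording, a few more serious adverse event reports and monitor reviews, and a slightly higher reported SAE count. The events are already collected for Aim 3 in patients with no ICA or a negative ICA, and the Section 8.6 interview covers later interventions.

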15.2 Recording of Adverse Events

At the follow-up contact with the subject, the study coordinator will seek information on adverse events by specific questioning and, as appropriate, by referral to a study coordinator for examination. Information on all adverse events should be recorded immediately in the source document, and also in the appropriate adverse event module of the case report form (CRF). All clearly related signs, symptoms, and abnormal diagnostic procedures results should be recorded in the source document, though should be grouped under one diagnosis.

All adverse events occurring during the study period will be recorded. The clinical course of each event should be followed until resolution, stabilization, or until it has been determined that the study treatment or participation is not the cause. Serious adverse events that are still ongoing at the end of the study period will be followed up to determine the final outcome. Any serious

adverse event that occurs after the study period and is considered to be possibly related to the study treatment or study participation will be recorded and reported immediately.

15.3 Reporting of Serious Adverse Events

15.3.1 Study Sponsor Notification by Investigator

This is an investigator initiated trial funded by a charitable contribution from a grateful patient. There is no study sponsor outside of Northwell Health.

15.3.2 EC/IRB Notification by Investigator

Reports of all serious adverse events (including follow-up information) will be submitted to the EC/IRB according to their policies. Copies of each report and documentation of EC/IRB notification and receipt will be kept in the Clinical Investigator's binder.

15.4 Unblinding Procedures

This is not a blinded clinical trial. Blinding in this study will not affect patient outcome, and, therefore, no unblinding is necessary. Cardiologists will interpret CCTA scans without access to FFR results. This is standard of care, and the interpretation will be necessary to determine which cases should be sent for FFR. The FFR is a computerized procedure. At the time the procedure is run, the computer operator will not know the exact level of obstruction documented by the cardiologist. This information is irrelevant to the operations of the computerized procedure and will not change the outcome of the CT-FFR test or the follow up patient care.

15.5 Stopping Rules

This study is low risk to patients, because essentially, it requires the use of protocols that are currently in place and represent standard of care. There may be a few instances in which a Cardiac Catheterization might be recommended for a patient who would not have received one if not a study participant. If the patient's cardiologist documents concern regarding patient safety if a Cardiac Catheterization were to be performed, the procedure will be discontinued.

15.6 Medical Monitoring

It is the responsibility of the Principal Investigator to oversee the safety of the study at his/her site. This safety monitoring will include careful assessment and appropriate reporting of adverse events as noted above, as well as the construction and implementation of a site data and safety-monitoring

plan (see section 17 Auditing, Monitoring and Inspecting). Medical monitoring will include a regular assessment of the number and type of serious adverse events.

15.7 Data and Safety Monitoring

Only one of the following three sections needs to be included in the protocol.

15.7.1 Data and Safety Monitoring Plan

[name]. will conduct data safety monitoring for the study.

His role as Director of the Cardiac Catheterization program at Lenox Hill Hospital makes him the most appropriate person to review the study safety, because he will have the most complete information on the cardiovascular condition of the patient, and the patients response to invasive ICA, the primary study activity that has potential to influence patient safety.

The expected types of events that will be monitored include major adverse cardiac events resulting from any Cardiac Catheterization, Percutaneous Coronary Intervention, or Coronary Artery Bypass Graft in a patient who, if not enrolled in the study, would not have received Cardiac Cath or invasive treatments. In addition, the monitor will review any medical complications for these subjects. The study coordinator will refer all patients who received Cardiac Cath, who would not have otherwise have received it if not part of the study. The monitor will review whether adverse events were the result of the study activity or related to procedures provided as part of standard of care, and whether safety policies and procedures were followed within one week of the all referrals. The monitor will present any recommendations for changes to the study resulting from the review to the study PI.

The monitor will conduct reviews as near as possible to the time the event was identified and always within a month of the identification of the event.

We do not expect to need to alter or interrupt the study design, because of the very low risk nature of the study. However, any unexpected safety events related to the study design will be carefully reviewed by the Safety Monitor and the study PI and reported to the IRB and Hospital quality assurance. If improvement in patient safety can be made by changing the design, immediate consideration will be given to the prospective change.

There are no issues with toxicity in this study.

If the study should be temporarily suspended, we will report this to the IRB, Clinical trials.gov, and to HeartFlow.

16 Data Handling and Record Keeping

